Protocol Synopsis

Singing and Cardiovascular Health in Older Adults PRO: 35864

PI: [name]

Protocol Synopsis

Brief Summary (up to 5,000 characters)

Cardiovascular disease (CVD) claims more lives each year than cancer and chronic respiratory disease combined. Participation in cardiac rehabilitation (CR) reduces mortality and risk of a major cardiovascular event in secondary prevention populations, including older adults. Older adults are less likely to participate in CR, as comorbidities in this population, including arthritis and chronic obstructive pulmonary disease, make participation difficult. Singing is a physical activity that involves components of the vagal nerves manifested as changes in cardiac autonomic regulation. Unlike physical exercise, the effects of singing on cardiovascular health has not been well-studied. To our knowledge, no studies have evaluated the impact of singing on important cardiac biomarkers. Our hypothesis is that older patients with CVD will have favorable improvement in cardiovascular biomarkers, including, endothelial function and heart rate variability (HRV), after 30 minutes of singing. Our pilot data in 23 subjects provides proof of principle, with a small, but significant, improvement in peripheral vascular endothelial function (measured by peripheral arterial tonometry) after 10 minutes of singing. This pilot study has helped us optimize the clinical trial design for this proposal, which will include a more targeted population, incorporation of personal music preferences, increased duration of singing, inclusion of a music therapist and measurement of brachial artery flow-mediated dilation (FMD), the “gold standard” measurement for vascular endothelial function, as our primary outcome. Our proposal seeks to create, optimize and test two different singing interventions in older patients with CVD.

The study will consist of three arms, according to a randomized, single-blind, crossover, sham procedure-controlled design. Sixty-five total participants will each have three visits on three different occasions for the following interventions: (1) a 30-minute period of guided singing from an in-person music therapist, (2) a 30-minute period of singing along to an instructional video including a professor of voice and “inexperienced, older singing student” and (3) a 30-minute rest period without any intervention. We will use biofeedback (target heart rate and BORG Rating of Perceived Exertion) to help subjects optimize the cardiovascular impact of the music interventions. The (2-year) R61 phase of this proposal will assess the feasibility (implementation, practicality, and acceptability) of executing the proposed study design (Aim 1). We anticipate that the R33 phase will take 3 years to complete. The combined R61/R33 phases will be statistically powered to assess changes in FMD and HRV (primary and secondary outcomes, Aims 2a and 2b). An alternative mechanism in Aim 3 will explore the impact of singing on mental health and well-being by measuring salivary cortisol and cytokines and by using a validated visual mood score designed to evaluate performing arts activities in healthcare settings. We will determine which singing intervention, if any, is superior to the other – as this would be important to guide longer and larger clinical trials in the field. Knowledge gained from this proposal will improve our understanding of biologic mechanisms of singing behaviors, as it relates to CVD.

Study Design Narrative Study Description (up to 32,000 characters)

The intent of this protocol is to evaluate the impact of singing on important cardiac biomarkers, including endothelial function, a marker of cardiovascular health and future cardiac risk.

The study is designed to consist of an initial phone screen and three study visits. The study will consist of three arms, according to a randomized, single-blind, crossover, sham procedure-controlled design. Sixty-five total participants will each have three visits on three different occasions for the following interventions: (1) a 30-minute period of guided singing from an in-person music therapist, (2) a 30-minute period of singing along to an instructional video showing

a professor of voice and “inexperienced, older singing student” and (3) a 30-minute rest period without any intervention.

Study staff will be provided a list of already pre-qualified subjects via an Honest Broker Tool through The Medical College. Study staff will then screen potential subject’s charts to determine eligibility. Providers will be messaged asking if they are appropriate. If yes, potential subjects will learn of this study via phone call or email from the study team. If a potential subject indicates that they are not interested, their information will not be saved, and they will not be contacted further. All private health information will be kept in a locked file cabinet in a locked office. All electronically stored information will be stored on a password protected computer with standard encryption software only accessed by those working directly on this project. The study team will first screen the potential subject via a phone conversation.

Once the subject is deemed eligible based on the eligibility criteria, he/she will be mailed a copy of the Institutional Review Board consent form to review. If after reviewing information about the study, the potential subject remains interested, randomization will occur and the first study visit (in the Adult Translational Research Unit) will be scheduled. Recruited subjects will be advised to remain fasting (for a minimum of at least 3 hours) until their research study appointment has been completed. The FMD procedures require an 8 hour fast, and the PAT procedures need only at least a three hour fast. For all study visits the subjects will be asked to remain fasting for 8 hours prior to their scheduled visit, they can have as much water as needed.

The informed consent signing/review will occur at the first study visit. Baseline vital signs (resting heart rate, blood pressure, pulse oximetry), weight and height will be obtained. Blood pressure will be measured from the subject's control arm (dominant arm preferred). The appropriately-sized (Bluetooth-capable) Heart Rate Variability (HRV) heart rate sensor strap will be applied to the subject. Subject's positional comfort will be maximized in the supine position. Baseline measurements of heart rate variability (HRV), brachial artery flow-mediated dilation (FMD) and peripheral arterial tonometry (PAT) will be collected by the research coordinator and specialized vascular sonographers as per detailed protocols.

The research team member will assist the subject in completing the study questionnaire, including demographics, medical history, current medications, current exercise and singing habits and physical limitations and/or mobility issues. A target heart rate (60% of 220-age) will be calculated. The subject will be educated on the BORG Rating of Perceived Exertion and target heart rate goals for singing. A visual analog mood score (ArtsObs) will be obtained prior to singing (or sham) intervention. Baseline salivary samples will be obtained (for cortisol and cytokines). The subject will be moved to a seated position for the singing intervention.

Subjects will undergo the following three interventions (separate Visits 1-3) in a cross-over design, separated by a minimum of 2 days (to allow for wash-out effects of the prior intervention):

1. Singing intervention 1 (instructional sing-a-long video): A video series will be created and recorded for the purposes of the study. The videos will include a vocal warm-up (10 minutes long). The subject will then have the option to select and sing two songs (10 minutes each), with offerings in four music genres including Folk, Pop, Country, and a Hymn. Each piece will vary in tempo, melodic contour, and rhythm. The total duration of singing via this format will be 30 minutes. The videos will be led by [name], Associate Professor of Voice and Voice Area Head at the University of Wisconsin-Milwaukee, with an inexperienced, older singer participating in the music making.
2. Singing intervention 2 (in-person music therapy session): Intake forms will be distributed to participants prior to starting music therapy for these sessions. These forms are used

to assess musical preference, prior music experiences as well as any medical conditions to take into consideration. Music therapy sessions will begin with vocal and breathing warm-up exercises for about 10 minutes. Upon completion of these exercises, subjects will choose a preferred song to sing from the multi-genre binder that the music therapist (MT) created specifically for this research based on age and preferences of patients.

The MT will play the songs for the subject to sing along to and will alter the characteristics of the music (volume, tempo, level of support) to ensure a successful experience for subjects and motivate them to put forth more effort into singing the song. The music therapist will continue to coach throughout the 30-minute session, reminding subjects of strategies practiced and how to implement those strategies while singing (i.e. maintain proper body alignment, breathe with the diaphragm as opposed to chest and shoulders, etc). Music therapy sessions will be led by [name], MT-BC, WMTR, Owner of Healing Harmonies Music Therapy, or a member of her team. [name] and her team of MTs were trained in Neurological Music Therapy by [name], one of the workshop panel of experts at the 2016 John F. Kennedy Center for the Performing Arts event that served as the catalyst for the current funding opportunities to promote research on music and health.

3. Control/sham intervention: Subjects will have a 30-minute period of rest sitting upright (as they would be positioned for the singing interventions). During this “rest” period, they will not be allowed to sleep, watch television, read, listen to music, converse with research team members, or even use their smart phones. This arm is meant to isolate the specific effects of the treatment rather than the potential “incidental” effects related to the research setting and measurements.

Target goals for both singing interventions will include at least one the following: (1) achieving at least 60% of maximum age-predicted heart rate (calculated as 220-age), or (2) reaching Borg Rating of Perceived Exertion intensity of 11 or higher. This will ensure at least a light-moderate level of exertion for singing activities to strengthen impact on cardiovascular biomarkers and outcomes. HRV recordings will be obtained or the duration of the singing interventions (or 30 minutes for the control intervention). One set of vital signs (heart rate, blood pressure, and pulse oximetry) will be recorded within the last 5 minutes of the singing intervention). After 30 minutes of intervention/control, the subject will be moved to the supine position where repeat measures of brachial artery flow-mediated dilation (FMD) and peripheral arterial tonometry (PAT) will be obtained. Additional salivary samples will be obtained (for cortisol and cytokines) after singing. A third set of vital signs will be recorded .A “post-singing” visual analog mood score (ArtsObs) will be obtained after the intervention. The entire ArtsObS instrument will be completed. Two reactions (relaxation and distraction) will be scored by the research coordinator nurse based on direct observation of the subjects during the singing intervention. The qualitative portion of this instrument enables the collection of personal feedback and quotations from subjects. Observers (research team) can also gather more detailed accounts of subjects' responses to activities, including experience and perceptions. At Visit 3, the research team will subjectively ask each subject about which (if any) singing intervention they preferred and why.

Interventions (<1,000 characters)

1. Singing intervention 1 (instructional sing-along video): Videos will include a vocal warm-up (10 minutes). The subject will select and sing two songs (10 minutes each), with offerings in four music genres including Folk, Pop, Country, and a Hymn. The total duration of singing will be 30 minutes. The videos will be led by [name], Associate Professor of Voice, with an inexperienced, older singer participating in the music making.
2. Singing intervention 2 (in-person music therapy session): Music therapy sessions will begin with a 10-minute warm-up. Subjects will choose songs to sing from a multi-genre binder. The music therapist (MT) will play the songs for the subject to sing along to while coaching the subject for a total of 30 minutes.
3. Control/sham: Subjects will have a 30-minute period of rest sitting upright, during which they will not be allowed to sleep, watch television, read, listen to music, converse with research team members, or use their smart phones.

FMD description

FMD is considered the gold-standard for non-invasive measurements of endothelial function. Vascular function is an important factor in the pathogenesis of atherosclerosis, hypertension and heart failure. Endothelial function, a marker of cardiovascular health and future cardiac risk, can be measured non-invasively with minimal to no risk to the subject. Brachial artery FMD is also highly predictive of coronary endothelial function and is a powerful indicator of vascular inflammation and future cardiovascular events. FMD measurement is attractive because it is non-invasive and allows for repeated measurements. Both diameter and blood velocity are assessed before and after brachial artery occlusion with a blood pressure cuff and results are reported as a change from baseline. Observational data from large population studies have demonstrated that abnormal FMD is associated with a higher rate of incident adverse cardiovascular disease events during a 5-year follow-up period.

## Statistical Design and Power

**Brachial artery FMD.** FMD is expressed as the change in post-stimulus diameter as a percentage of the baseline diameter (FMD%). Our primary outcome is percent brachial flow-mediated dilation (FMD%). We employ a cross-over design since the most powerful test will compare the same subjects against themselves (i.e., avoiding many potential inherent subject differences). In a scenario with no anticipated differences, FMD correlations were observed to be 0.8 at 12 weeks (95% CI: 0.72, 0.87). Therefore, assuming an auto-regressive structure, we assume the correlation would be 0.64 at 26 weeks and 0.41 at 52 weeks. For a 25% relative difference (2% absolute difference) in FMD with 90%

Difference between groups	Power (alpha 0.05)	N	N plus 25% dropout
0.010	0.90	114	143
	0.80	86	108
0.015	0.90	52	65
	0.80	40	50
0.020	0.90	30	38
	0.80	23	29

power and alpha 0.05, we would need just 30 subjects (comparing singing interventions to sham/control). But, to compare the singing interventions to each other, using a delta of 0.015, we will need 52 subjects for 90% power and alpha 0.05. To have 52 evaluable subjects (assuming a 25% dropout rate), we will enroll 65 subjects. Please refer to the sample size table (shown above). We will be powered for all primary (FMD) and secondary outcomes (PAT and HRV). All outcome variables over 3 visits will be compared using analysis of variance (ANOVA) with repeated measures. The exposure variable is the singing (or sham) interventions.

**PAT measurements.** *EndoPAT* is the FDA-cleared non-invasive test and device that provides an index of endothelial function in two forms: reactive hyperemia index (RHI) and LnRHI. The RHI is the post-to-pre-occlusion PAT signal ratio in the occluded side, normalized to the control side and further corrected for baseline vascular tone. Normal values for RHI are  $>1.67$ . In our small, pilot study, the average baseline RHI for 23 subjects was  $1.93 \pm 0.13$  (range: 0.93 to 3.62). There was a trend toward improvement to  $2.06 \pm 0.15$  – though we were underpowered for statistical significance. The LnRHI provides a better double-sided distribution than RHI that is closer to normal distribution. It offers better separation between disease states. The PAT ratio is the natural logarithm of the ratio of the post-deflation to baseline pulse amplitude in the hyperemic finger divided by the same ratio in the contralateral (control) finger. This ratio is based on the 90- to 120-second post-deflation interval, which had the strongest correlation to cardiovascular risk factors in the Framingham Heart Study cohort. We saw a significant improvement in the PAT ratio in our 23 subjects. We aim to confirm this finding with this study proposal, which is appropriately powered for both RHI and the PAT ratio.

We were unable to locate the reliable figures for within subject correlation measures of either the RHI or the PAT ratio in order to compute their power in a cross-over design. Fortunately, due to the size of the changes anticipated, sample size calculations for simple comparisons yield values similar to those planned. For example, given a change of 0.08 with 0.1 standard deviation in RHI, a sample size of 52 would yield a power of 81% with alpha 0.05. Therefore, in a cross-over design, we would be able to detect a change of 0.08 with power greater than 81% or we would be able to detect changes less than 0.08 with power equal to 81%. Similar remarks can be made for the PAT ratio.

**HRV measurements.** The normal-to-normal (NN) intervals include all intervals between adjacent ECG QRS complexes resulting from sinus node depolarizations. Standard measures of HRV (time domain analysis) include the standard deviation of all NN intervals (SDNN), the square root of the mean of the sum of the squares of differences between adjacent NN intervals (RMSSD), the natural log (ln)RMSSD and HRV score.

For RMSSD, we also do not have reliable correlation numbers. However, for a simple comparison with a change of 15 and a standard deviation of 22.5 (based on our preliminary data), we would arrive at 65% power with a sample size of 52. Therefore, in a cross-over design, we would obtain more power and/or be able to detect smaller differences.

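### The dropout allowance multiplies N by 1.25 instead of dividing by 0.75: 65 enrolled leaves 48 or 49 evaluable at 25% dropout, not 52, and about 88% power for singing versus singing, not 90%

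*SAP*

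**What the plan says.** In the SAP, Statistical Design and Power, the Brachial artery FMD paragraph gives a sample size table for three differences (0.010, 0.015, 0.020) at 90% and 80% power. Detecting 0.020 between singing and sham with 90% power takes 30 subjects. The comparison of the two singing interventions is the demanding one: "using a delta of 0.015, we will need 52 subjects for 90% power and alpha 0.05". Enrolment follows from it: "To have 52 evaluable subjects (assuming a 25% dropout rate), we will enroll 65 subjects". The last column of the table, headed "N plus 25% dropout", gives 143, 108, 65, 50, 38 and 29 for N = 114, 86, 52, 40, 30 and 23.

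The protocol synopsis (Brief Summary) gives the same total of 65 and lists deciding whether one singing intervention beats the other among the study's goals.

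The number 52 is used again under PAT measurements, for RHI ("a sample size of 52 would yield a power of 81% with alpha 0.05"), and under HRV measurements, for RMSSD ("we would arrive at 65% power with a sample size of 52").

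**The concern.** A dropout rate is a fraction of those enrolled. To end with N evaluable subjects after losing a fraction d, one enrols N/(1 − d). The SAP enrols N × (1 + d), which is always smaller. On the SAP's own dropout assumption, the trial therefore does not deliver the evaluable number in the sentence that justifies its size, nor the power attached to that number.

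The shortfall lands on the contrast that raised the required number from 30 to 52. A reader who relies on the sentence will believe that 25% loss is already covered at 90% power, when only 20% loss is.

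**Working it through.** **Inputs from the SAP (Brachial artery FMD):** N = 52 evaluable, difference 0.015, power 90%, alpha 0.05 (sidedness not stated), dropout 25%, enrolment 65, and the six rows of the table. No standard deviation of FMD or of the paired difference is given.

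**Step 1. Reproduce the dropout column, then correct it.**

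| Difference | Power | N | SAP column | N × 1.25, rounded up | N / 0.75, rounded up |
|---|---|---|---|---|---|
| 0.010 | 0.90 | 114 | 143 | 143 | 152 |
| 0.010 | 0.80 | 86 | 108 | 108 | 115 |
| 0.015 | 0.90 | 52 | 65 | 65 | 70 |
| 0.015 | 0.80 | 40 | 50 | 50 | 54 |
| 0.020 | 0.90 | 30 | 38 | 38 | 40 |
| 0.020 | 0.80 | 23 | 29 | 29 | 31 |

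Multiplying by 1.25 returns all six printed entries exactly.

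**Step 2. What 65 enrolled delivers.**
- Evaluable at 25% dropout: 65 × 0.75 = 48.75, so 48 or 49.
- Enrolment needed for 52: 52/0.75 = 69.3, so 70.
- Dropout that 65 covers: 1 − 52/65 = 20%.
- If each subject drops out independently with probability 0.25, the chance that at least 52 of 65 remain (binomial) is about 22%.

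**Step 3. Recover the standard deviation behind the table.** For a two-sided paired t-test, power = P(T > t) where t is the 97.5% point of the t distribution with n − 1 degrees of freedom and T is noncentral t with noncentrality (difference/SD) × √n. An SD of the paired difference between 0.03259 and 0.03265 returns all six Ns (114, 86, 52, 40, 30, 23). Values just outside fail: 0.0325 gives 113 in the first row and 0.0327 gives 115. A one-sided test does not fit: no SD searched from 0.033 to 0.040 returns all six (the closest gives 114, 83, 52, 38, 30, 22).

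**Step 4. Power at the evaluable number actually left.** For example, with SD 0.0326 and n = 48, the noncentrality is (0.015/0.0326) × √48 = 3.19; with n = 52 it is 3.32.

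| Evaluable | Power for 0.015 | Power for 0.020 | Difference detectable with 90% power |
|---|---|---|---|
| 52 (as stated) | 90.2% to 90.3% | 99.1% | 0.0149 to 0.0150 |
| 49 | 88.3% to 88.4% | 98.8% | 0.0154 |
| 48 | 87.6% to 87.8% | 98.6% | 0.0156 |

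**Step 5. The other places that use 52.** The RHI figure (change 0.08, SD 0.1) and the RMSSD figure (change 15, SD 22.5) reproduce as two-sample t-tests with 52 split into two groups of 26: 81% and 65%. With 48 split into two groups of 24 they become 77% and 62%.

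**The case against.** The strongest reply is that little turns on this. One contrast loses about 2 points of planned power, its detectable difference moves from 0.015 to about 0.0155, and singing versus sham is untouched in practice. That is a fair account of the size. It does not make the sentence true.

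The 88% can also be called slightly pessimistic. The SAP plans a repeated-measures ANOVA over three visits. With a pooled error term on 2(n − 1) degrees of freedom, and sphericity assumed, the same SD of 0.0326 gives 88.4% at 48 and 89.0% at 49. A subject who leaves after two visits may also still supply the singing-versus-singing pair. Both remarks are sound, and the second is a reason to define evaluable. But the pooled figures still miss 90%, and no reading of the analysis turns 65 less 25% into 52.

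The column heading, taken alone, could mean N plus a 25% margin. The enrolment sentence closes that reading, because it names a dropout rate and the number left after it.

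Finally, the RHI and RMSSD figures are stated as conditional on 52 and are correct at that number on a two-group basis. The SAP presents them as floors that the cross-over would exceed. In this design each evaluable subject is measured under every condition, and even two independent groups of 48 would have 97% and 90% power. So the drops to 77% and 62% do not describe the trial's real power. They show only that the printed numbers rest on an evaluable count that the plan does not deliver, which makes this a secondary point.

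**Conclusion.** The concern holds. That 65 enrolled does not leave 52 evaluable at 25% dropout follows from the SAP's own figures and needs no assumption. The result is 48 or 49, and 70 would be needed for 52.

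The effect on power is small: about 88% instead of 90% for the 0.015 contrast, and still above 98% for 0.020. These power figures assume a two-sided test, complete cases only, and an SD of the paired difference of about 0.0326 inferred from the table. That one value returns all six rows, so the inference is well supported, but the SAP does not state it. The error should be corrected because it sits in the sentence that justifies the trial's size; it does not threaten the design.

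**What to change.** Keep 65 enrolled and the 25% dropout assumption, and make the stated figures agree with them:

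- Replace the enrolment sentence with one to this effect: 65 will be enrolled; at 25% dropout about 48 will be evaluable, giving about 88% power for a 0.015 difference between the singing interventions and more than 98% for 0.020 against sham.
- Correct the dropout column to 152, 115, 70, 54, 40 and 31, with a footnote that planned enrolment (65) is below the 70 in the bolded row.
- Define evaluable: all three visits completed, or both visits of the contrast in question.
- Under PAT and HRV measurements, restate the power at the evaluable number adopted, and say that the calculation treats it as two independent groups.

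Alternatively, if the sponsor can justify 20% dropout, leave the numbers as they are and relabel both the column and the sentence as 20%. Enrolling 70 would also restore 52 evaluable (70 × 0.75 = 52.5), at the price of five more participants; a 2-point shortfall does not require it.

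The recommended change costs SAP wording only. One stated power becomes about 2 points less favourable, with no extra enrolment and no change of analysis.

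### The visible SAP does not say whether post-session FMD% or the pre-to-post change is analysed; a within-participant adjusted mixed model with robust standard errors, using all completed visits, would be a cheap gain in efficiency.

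*SAP*

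**What the plan says.** The SAP, under Statistical Design and Power (Brachial artery FMD), names FMD% as the primary outcome. The change in its definition of FMD% is the cuff response within one scan, not the change across a session. The visible analysis plan is two sentences: "All outcome variables over 3 visits will be compared using analysis of variance (ANOVA) with repeated measures" and "The exposure variable is the singing (or sham) interventions".

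The contrast that sets the sample size is singing against singing: "to compare the singing interventions to each other, using a delta of 0.015, we will need 52 subjects". Its inputs are correlations of FMD between occasions: 0.8 observed at 12 weeks, from which "we assume the correlation would be 0.64 at 26 weeks and 0.41 at 52 weeks". Enrolment follows: "To have 52 evaluable subjects (assuming a 25% dropout rate), we will enroll 65 subjects".

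The protocol's Study Description has FMD and PAT measured on both sides of the session. Before it, "Baseline measurements of heart rate variability (HRV), brachial artery flow-mediated dilation (FMD) and peripheral arterial tonometry (PAT) will be collected"; after it, "repeat measures of brachial artery flow-mediated dilation (FMD) and peripheral arterial tonometry (PAT) will be obtained". The pre-session scan is described in the first-visit narrative. The fasting instruction, "For all study visits the subjects will be asked to remain fasting for 8 hours prior to their scheduled visit", fits a pre-session scan at every visit, but the protocol does not say so outright. The Brief Summary describes the study as powered for changes in FMD and HRV, which leans towards a change score without defining the analysed variable.

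**The concern.** Two analysts could follow this text and run different primary analyses, one on post-session FMD% and one on the pre-to-post difference. Both are valid in a crossover, but their variances differ. Which is smaller depends on the same-visit pre-post correlation, which the documents do not give.

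A third option uses the same measurements: analyse the post-session value and adjust for the pre-session value within participant. If pre-post correlation is similar across interventions, this is at least as precise as either alternative, apart from about 1-2% of variance. A mixed model can also keep completed visits from people who leave early, which matters when 25% dropout is expected. At stake is precision in the primary comparison, and a primary variable fixed in advance.

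**Working it through.** **1. Reproduce the plan's table.** No SD is stated and two-sided testing is assumed. With SD 0.03 (inferred) and between-visit correlation rb = 0.41, the SD of a paired difference is 0.03 × √(2 × (1 − 0.41)) = 0.0326. A two-sided paired t-test at 0.05 then needs:

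| Difference | 90% power | 80% power |
|---|---|---|
| 0.010 | 114 | 86 |
| 0.015 | 52 | 40 |
| 0.020 | 30 | 23 |

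All six entries match. The table fixes only the difference SD, however. SD 0.0386 with correlation 0.64, or 0.0518 with 0.80, gives about 0.0327 and nearly the same table. So does any change score with that difference SD.

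**2. Compare the analyses, if 52 was sized on post-session values.** Let rw be the same-visit pre-post correlation (assumed). In units of SD², the contrast variances are:

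- post-session value: 2(1 − rb)
- change score: 4(1 − rw)
- within-participant adjusted: 2(1 − rb)(1 − r²), with r = (rw − rb)/(1 − rb)

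At SD 0.03, rb = 0.41, n = 52 and difference 0.015:

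| rw | r | SD of contrast: post / change / adjusted | Power: post / change / adjusted |
|---|---|---|---|
| 0.41 | 0 | 0.0326 / 0.0461 / 0.0326 | 90.3 / 63.4 / 90.3% |
| 0.64 | 0.39 | 0.0326 / 0.0360 / 0.0300 | 90.3 / 83.8 / 94.2% |
| 0.80 | 0.66 | 0.0326 / 0.0268 / 0.0244 | 90.3 / 97.7 / 99.1% |

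Change scores break even with post values at rw = (1 + rb)/2 = 0.705. If SD is 0.03 but rb is 0.64, post values already give 98.6%; at rb = rw = 0.80 every choice gives at least 97.7%.

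**3. If 52 was sized on change scores instead.** Change variance is 2(1 − r) times the post variance, and adjusted variance is (1 − r²) times it. At r = 0 / 0.25 / 0.5 / 0.75, post values alone need 28 / 36 / 52 / 103 participants for 90% power, and adjustment needs 28 / 34 / 40 / 46.

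**4. The participant mean is essential.** Simulation: n = 52 complete, six balanced sequences, random-intercept model, 5,000 runs per case, simulation error about 2% on each ratio. Where adjustment can gain nothing (rw = rb = 0.41 / 0.64 / 0.80), variance relative to post values was 1.01 in all three cases with the participant mean included. With the raw pre-session value alone it was 1.11 / 1.26 / 1.54.

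**5. Missing visits.** Of 65 enrolled, 25% is about 16, leaving 49 completers. Post values in 49 completers give 88.4% power. With 8 people assumed to leave after visit 1 and 8 after visit 2, completely at random (rb = 0.41), all visits without adjustment give 91.3%. All visits with adjustment give 91.2 / 95.5 / 99.3% at rw = 0.41 / 0.64 / 0.80. Type I error here, with equal correlations across interventions, was 4.4-5.4%.

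**6. Unequal correlations.** Suppose the within-visit pre-post correlation is 0.83 under sham and 0 to 0.39 under both singing interventions. With one common slope and pooled residual variance, simulated type I error for singing against singing is about 7-8%, against about 5% unadjusted. Participant-clustered robust standard errors bring it to about 5.3-5.7%. The adjusted variance is 1.09-1.10 times that of post values when the singing correlation is 0, equal at about 0.2, and 0.87-0.89 at 0.39.

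**The case against.** The strongest objection concerns the remedy. A common slope for the pre-session value, with residual variance pooled over interventions, is anti-conservative for the very contrast that sets N when sham is more repeatable than singing. That pattern is plausible, since rest should alter FMD less. This stands, and it is why the sentence below specifies robust or intervention-specific variance.

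A reader might infer that 90% power holds only if one FMD% per condition is compared, or that the trial is underpowered. The documents support neither. The table fixes only a difference SD, which could describe change scores, and a change score reaches 97.7% at rw = 0.80. The 0.41 is the assumed 52-week correlation, whereas visits need be only 2 days apart. If the correlation is higher at SD 0.03, power may already be ample.

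A reader might also infer that the SAP discards participants with missing visits. It does not say so; that is the usual behaviour of a classical repeated-measures ANOVA. The gain from all visits without adjustment is about 3 points (88.4% to 91.3%).

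The unavailable SAP text could define the analysed value, so the omission is established only for the visible text. The adjustment also needs pre-session scans at every visit. Both limits are real, but neither removes the benefit of naming the variable and using the measurements described.

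**Conclusion.** The point holds as a recommended efficiency improvement, with medium confidence. The repeated-measures ANOVA is a valid crossover analysis, and a reader who takes this as an analysis error goes beyond the documents.

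If the table was sized on post-session FMD% with SD 0.03 and between-visit correlation 0.41, power at n = 52 ranges from 63% to 98% for change scores over the pre-post correlations considered. Post values stay at 90%, and the adjusted analysis ranges from 90% to 99%. Adjustment therefore removes most of the dependence on an unknown correlation. The actual gain cannot be stated, because the SD, the pre-post correlation and the timing of dropout are all assumed or back-solved.

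**What to change.** Unless other SAP text already covers this (in which case align the two), add after the ANOVA sentence:

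> For FMD% (primary) and PAT, post-session values will be analysed with a linear mixed model with fixed effects for intervention, period, same-visit pre-session value and the participant's mean pre-session value, and a random participant effect, using all participants with at least one post-session measurement. Standard errors will be participant-clustered robust with a small-sample correction (or residual variances will be allowed to differ by intervention). Pairwise contrasts with 95% CIs will be reported.

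Confirm that pre-session FMD and PAT are taken at all three visits. If they are taken only at visit 1, drop the two pre-session terms and state that post-session FMD% is analysed using all completed visits. The existing ANOVA sentence can stay for the other outcomes, including HRV, which is recorded during the session and does not fit a post-session template.

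The cost is one sentence, and no new measurements if the scans are already taken at each visit. The downsides are:

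- about 1% of variance when adjustment gains nothing
- up to about 10% of variance in the extreme unequal-correlation case
- slight small-sample imprecision of robust standard errors
- a missing-at-random assumption for incomplete participants
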